**Maternal Adversity, Vulnerability and Neurodevelopment (MAVAN)
Project**

Investigators:

Principle Investigator: [name]; Co-Investigators: [name], [name], [name], [name], [name], [name], [name], [name], [name], [name], [name], [name], [name], [name], [name], [name].

Project funded August 1, 2004 through a CIHR Strategic Grant (750,000 per year for 5 years)

Research Project

Submitted for Approval by Douglas Hospital REB

February 25th, 2004

I. Introduction.

Objectives: The probability of chronic illness is strongly influenced by environmental conditions prevailing during development (Hertzman 1999). The frequency of heart disease, diabetes, and mental illness is substantially greater amongst those born and raised in poverty, regardless of social class in adulthood. Adversity associated with poverty produces incomplete, dysfunctional families often rife with domestic violence, malnutrition, drug use, child abuse and neglect. Reproduction within this context is associated with maternal stress, increased risks for infection and thus pre-term labour, perinatal deaths, birth insults, poor nutrition for mother and offspring, and serious compromises in the quality of parent-child interactions. These conditions define high-risk families. For the child, these conditions bear the potential to influence the development of physiological systems that regulate metabolism and cardiovascular function, as well as neural processes underlying emotion and cognition. These effects form the basis for vulnerability for illness.

Perhaps the most dramatic illustration of the relation between adversity in early life and the risk for later illness emerges from studies on birth weight, early growth and health in adulthood. Individuals that were small for gestational age, suggesting some degree of intrauterine growth restriction, are at significantly greater risk for type II diabetes, visceral obesity and hypertension (collectively referred to as the metabolic syndrome). The major predictors of fetal growth restriction and pre-term labour, are maternal stress, infections, malnutrition, and tobacco/alcohol consumption. These risk factors are far more prevalent in low socio-economic status (SES) families and, predictably, low SES is a major risk factor for both intrauterine growth retardation (IUGR) and pre-term labour.

It is increasingly clear that growth restriction also predicts an increased risk for mood disorders (Thompson et al. 1997, and see Kelly et al. 2001). Additionally, the risk factors (i.e., maternal stress, tobacco/alcohol use, nutritional deprivation) for IUGR are also the major predictors for Attentional Deficit Disorder (ADD) and, predictably, ADD is far more prevalent in low SES environments (Biederman et al., 1990, 1995; Barkley 2000). Follow up studies of growth retarded infants reveal evidence for problems associated with attention and impulse control, functions that are heavily dependent on the hippocampus and prefrontal cortex. These same brain regions are also among the major sites implicated in both depression and anxiety disorders. Interestingly, growth restriction is also associated with increased behavioural inhibition, shyness and timidity in childhood, all of which appear to be predictors of mood disorders in later life. Studies with primate and rodent models show that the development of the hippocampus is impaired by fetal glucocorticoid exposure or by prenatal stress, and glucocorticoids are a mechanism for fetal growth restriction.

Glucocorticoids are a major class of stress hormones and the release of these hormones is activated by stress, as well as by protein deprivation, tobacco and alcohol. Thus, we propose *that impairments in the development of the hippocampus and prefrontal cortex serve as the mechanism for the relation between fetal growth restriction and impaired cognitive and emotional development.*

These studies suggest that endocrine conditions that promote fetal growth restriction can also compromise neural development. However, follow-up studies with even very low-birth weight babies reveal an impressive level of variability in cognitive outcomes. Evidence from clinical intervention studies with high-risk infants and developmental neurobiology suggests that neurocognitive development is influenced by the quality of the postnatal environment. Of particular relevance are the results of studies with primate and rodent models indicating that nurturing forms of maternal care can enhance neuronal survival and synaptic growth in regions such as the hippocampus (see below). Thus we propose *that the developmental outcomes associated with fetal adversity, reflected in growth retardation, are determined by the quality of the postnatal environment.*

Longitudinal studies reveal early life markers of poor health outcomes over the lifespan that include low birth weight, irritable temperament in early childhood and poor frustration tolerance, parental stress, attentional deficits and even increased blood pressure. These conditions can be quantified and we propose to use such measures in the development of longitudinal studies on the interactions between prenatal and postnatal environmental conditions in predicting health outcomes. **Specifically, we will investigate influences of the early environment (prenatal and early neonatal) on neuropsychological development. Our focus for the study of postnatal environment is on maternal well-being and mother-infant interactions. Hence our measures include not only functional assessment of the offspring, but also measures focusing on the mother. We feel that this study will provide a crucial basis for the development of focused, early intervention programs.**

Adverse Perinatal Environment: Development of Disease

There is a dramatic increase in the risk for coronary heart disease, obesity and diabetes (metabolic syndrome) among individuals who were small for gestational age, a condition that implies some measure of intrauterine growth retardation (IUGR) and adverse fetal environment ([name] 2001; Barker 2002; Seckl et al. 1999). The health risk appears linked to the programming effects on gene expression, especially that of hepatic genes. The conditions of risk associated with impoverished fetal life are not restricted to cardiovascular or metabolic disease. Adverse intrauterine environment has also been linked to neurodevelopmental disorders. Both prematurity and IUGR

are consistently associated with cognitive impairments; the existing data suggest that cognitive outcomes are more seriously compromised by growth restriction than by prematurity (Lagercrantz 1997). Studies using more global measures of cognitive development, such as IQ tests, reported significant impairments among IUGR children (e.g., Breslau et al. 1996; Fattal-Valevski et al. 1999; Leitner et al. 2000;). van der Reijden-Lakeman et al. (1997) found that at 2 years of age, IUGR children were impaired on tests of divided, focused and sustained attention. On such tests, the IUGR population was less accurate and more impulsive than controls. These findings suggest that low-birth weight children might be at greater risk for the development of Attentional Deficit Disorder (ADD). Indeed, the risk factors for IUGR, including maternal stress, maternal psychopathology, protein malnutrition, tobacco/alcohol consumption are identical to those for ADD. Likewise, maternal stress during gestation is a predictor of both fetal growth restriction and negative temperament (irritability, negative emotionality) and anxiety in children (O'Connor et al. 2000; Glover et al. 2002). Behavioural disorders, characterized by poor impulsive control, shyness, timidity and negative temperament (greater frequency of negative emotional states) are positively related to the degree of growth restriction (e.g., Szatmari et al. 1990; Pharoah et al. 1994; Sykes et al. 1997).

Adverse fetal environment affects the risk for chronic illness via direct and indirect pathways. In the case of the metabolic syndrome, direct effects include modification of the expression of enzymes involved in fat (PEPCK) and glucose (glucose kinases) metabolism. Intellectual and emotional development is affected by direct early environmental effects on neuronal proliferation and synaptogenesis in regions such as the hippocampus, amygdala and the frontal cortex. Indirect effects on metabolic and neurological function include programmed modification of neuroendocrine function, particularly the hypothalamo-pituitary-adrenal (HPA) axis, throughout the lifespan. Indeed, many of the pathologies associated with the metabolic syndrome are identical to those observed in patients with Cushing's syndrome (hypersecretion of cortisol; see McEwen et al. 1999; [name] & [name] 2001 for reviews). Furthermore, Cushing's patients are at increased risk of depression and cognitive impairment; both directly linked to dysregulation of HPA function. These observations indicate the central role of HPA function in perinatally programmed disease. In rodents, fetal adversity permanently increases corticotropin-releasing factor expression in the hypothalamus and amygdala; such effects appear to be mediated by alterations in the hippocampus and prefrontal cortex ([name] 2001). These changes are linked to life-long enhancement of stress reactivity, which serves to exacerbate the risk of developing metabolic and neurological disorders.

Fetal growth retardation is associated with problems of impulse control and attention. The preliminary results of recent imaging studies of low-birth weight children reveal significantly decreased hippocampal volume. Indeed,

alterations in hippocampal and prefrontal development might explain the unusually high level of comorbidity between attentional deficits - impulse control disorders and affective disorders. The hippocampus and prefrontal cortex are also critical structures for impulse control and emotional states such as fear. Importantly, each of the risk factors for IUGR is known to increase fetal adrenal release of glucocorticoids. Thus adversity during fetal development increases exposure to glucocorticoids, which are known to promote growth restriction and compromise neural development, resulting in vulnerability for both cognitive and emotional disorders (Fig. 1). For example, fetal exposure to glucocorticoids decreases neuronal proliferation in the hippocampus (Ono et al., 1989; McEwen 1999; Liu & [name] 2001). Interestingly, fetal dexamethasone administration in humans for congenital adrenal hyperplasia was associated with increased shyness and timidity in children. Both anxiety disorders and depression are accompanied by significant decreases in hippocampal volume and, in the case of depression, dramatically reduced volume and activity in the prefrontal cortex. The hippocampus and the prefrontal cortex are primary targets for both antidepressant and anti-anxiety medications.

The influence of environmental adversity on offspring development is not limited to the prenatal period. There is clear evidence for the importance of postnatal poverty and family dysfunction on child development and health. Importantly, the effects of socioeconomic status (SES) on emotional and cognitive development in children are mediated by variations in parental care (Conger et al., 1994; McLoyd et al. 1998). Indeed, when parental care factors are statistically controlled, the effect of SES is eliminated. Likewise, low SES is associated with elevated cortisol levels in children, and these effects are mediated by parental factors. This suggests that stress of poverty, which is linked to increased risk of adverse fetal development, also compromises the quality of childcare. In rodent and nonhuman primate models, mother-pup interactions regulate neurodevelopment and disruptions to mother-infant interactions are associated with impaired neurodevelopment and exaggerated HPA and emotional responses to stress ([name] 2001).

The influence of the postnatal environment is a sword that can, potentially, cut both ways. In the rat, more intense forms of maternal care, characterized by increased pup licking, promote hippocampal synaptic development and dampen HPA responses to stress ([name] 2001). In the rat, maternal licking causes an increase in neurotrophic factor expression, enhancing both neuronal survival and synaptic outgrowth (Liu et al. 2000; Bredy et al. in press). Increased maternal licking over the first week of life is also directly linked to more modest HPA and behavioral responses to stress (Francis et al., 1999; Caldji et al., 1998, in press). Likewise, in humans, nurturing family environments dampen stress reactivity and promote resistance to chronic illness. Such findings raise the possibility that conditions of the postnatal environment could offset or reverse the risk created during

fetal development. Indeed, in animal studies there is clear evidence that postnatal enrichment, for example, can serve to eliminate the effects of fetal adversity. This issue is obviously of profound significance for the development of early intervention studies.

II. Hypotheses.

Statement of the Problem: There is increasing evidence that many forms of chronic illness in child- and adulthood have perinatal origins. Developmental studies in both human and nonhuman subjects, have only very rarely examined the effects of environmental events at one stage of development in the context of previous experience.

Hypotheses: There is significant interaction between the prenatal and postnatal environment in programming child- and adulthood disease, and that careful manipulation of the infant environment can ameliorate or reverse the negative health outcomes associated with adverse intrauterine experience. *We hypothesize that the effects of fetal adversity on neurodevelopment are determined by the quality of the postnatal environment, particularly by mother-infant interactions. Moreover, we propose that the quality of mother-infant interactions is strongly influenced by maternal emotional well-being.*

III. Methods

Participants. Our approach will be to develop a human cohort derived from a study already nearing completion in Montreal (The Montreal Prematurity Study funded by the March of Dimes; PI: [name]). [name] is a collaborator on the MAVAN project, and Drs. [name] and [name] are collaborators on the Prematurity Study. The Prematurity study involves measures of psychosocial stress, nutrition, and family and community living conditions as predictors of gestational length, which is the outcome measure in this project. This project will recruit 5000 women at 13-15 weeks gestation, of which approximately 4000 have been recruited and will have given birth before the start of our project, leaving a population of 1200 potential subjects. Currently, 100 women each month are assessed at 24-26 weeks gestation. There is currently in place an infrastructure for follow-up of women from the Montreal Prematurity Study.

The cohort for the current MAVAN project will be derived from the same population used in the Prematurity Study. In essence the MAVAN Project will serve as a follow-up study derived from the Prematurity Study focusing on a substantially smaller population. The strategy for the MAVAN Project is to take advantage of the multivariate assessment of prenatal adversity in The Montreal Prematurity Study. We will follow infants born at normal weight (controls, n= 120; 3000-3500 g at birth) and low-

birth weight babies exhibiting evidence for intrauterine growth retardation (IUGR, n= 120; 2200-2750 g at birth). These groups are based on the recently published Canadian standards for fetal growth (Kramer, M. S., R. W. Platt, S. W. Wen, K. S. Joseph, A. Allen, M Abrahamowicz, B. Blondel, and G. Bréart. 2001. "A new and improved population-based Canadian reference for birth weight for gestational age." *Pediatrics* 108:), which indicates that the birth weight of 2,750 g represents the 10th percentile, with a weight of 3750 g at the 70th percentile. Our intent is to avoid extreme cases of growth retardation (i.e., < 2,200 g). All babies in this study will be born at > 37 weeks gestation to avoid the complication of prematurity and growth restriction. We will recruit two cases for each case (i.e., two infants of normal birth weight for each infant that is small for gestational age).

The method of recruitment for the MAVAN Study will follow the same procedures as another CIHR-funded follow-up study of the Prematurity Study. The New Mothers Study ([name], PI, [name], [name], [name], and [name] co-investigators) examines the physical and psychological well being of mothers during the first year post-partum with particular attention to mothers of babies born with health problems and mothers of low socio-economic status. The New Mothers Study is in its fourth year. Letters are sent to the mothers about the follow-up to the Prematurity Study with a rejection card and postage paid envelope. Women who do not wish to receive a phone call for the follow-up study simply put the rejection card in the envelope and in the mail. About 2 women per month choose this option. With a 9% prevalence rate of IUGR, we can expect that 126 IUGR babies from the Montreal Prematurity Study will be available as potential participants. Current recruitment rates (~70% participation) suggest that we will obtain a sample of 88 IUGR children and their mothers. Two, normal weight for age babies born on the same or closest day to the IUGR baby will be used as controls with a target of 252. Based on the differential prevalence rates of IUGR among low and high SES mothers, we can expect a sample of 31 low SES mothers and babies in the IUGR group and 57 high SES. Because SES (and associated chronic stressors and depression) may have an adverse effect on child development mediated by postnatal growth delay rather than by IUGR, we will oversample low SES babies who are normal weight for age at birth and consider their postnatal growth as an additional factor predicting cognitive development.

Overview

The measures described here assess the following domains: general development, attention/ impulsivity, social/emotional development, temperament, and basal and stimulated hypothalamic-pituitary-adrenal activity. Methods include measures of parental reports of infant behaviour;

direct testing of the infant, questionnaires for the mother, and observation of mother and infant. Direct testing of the infant occurs with the mother present up to the age of 36 months. At 18-months, 30-45 minutes of maternal testing will be conducted while the infant is cared for by a familiar laboratory assistant, *after* infant assessment (attention/impulsivity) is completed. By 36-months, infants can be assessed alone and therefore mother and infant assessments can occur simultaneously. Note, that individual research assistants are assigned to specific mother-infant pairs for which they will be responsible for the duration of the study. Our intention here is to allow individual assistants to become familiar with mothers/infants and thus ease the level of apprehension associated with testing.

The measures and procedures described here for the infants occur in parallel with those of the mothers. In this plan, we have considered the joint burden of assessment on mother and infant to ensure that: 1) home rather than laboratory visits predominate in the first year; 2) questionnaires are distributed over time; 3) no session is longer than 2 hours total; 4) the time required for individual infant tasks is within the limits appropriate to the age of assessment and 4) mother-child separations do not occur in the first 18 months, are no more than 30-45 minutes at 18 months, and no more than an hour at 36 months. During mother-infant separations, infants will remain with a familiar assistant. Few of the test materials included in this protocol comprise diagnostic tools. However, where appropriate (e.g. depression scales), subjects will be immediately notified if test scores suggest pathology and offered a referral to an appropriate mental health specialist.

Finally, we mention the possibility of brain imaging in children. However, the details of the procedure have not yet been finalized and would pertain only to the children of 36 months of age. Please note that we will conduct imaging only in unanesthetized subjects. Under no conditions would we consider the possibility of any sedative agent. The Montreal Consortium for Brain Imaging Research, of which [name], [name], [name], and [name] are members and [name] the Director, is the lead site for the NIH Developmental Brain Mapping project. The lead site for neuroimaging (structural MRI) of younger children is at Washington University in St. Louis. To date, this site has imaged ~150 children using no anesthetic or sedative and is the most experienced site in the world. We have had extensive consultation with this team and the information provided suggested that our original plan to image infants was unlikely to be feasible with the current CIHR budget. In contrast, they report remarkable success with children above 24 months (i.e., >70%), especially when children are prepared for scanning with experience in a Mock Scanner, which simulates the imaging conditions (noise, confinement, etc.) with the exception of the actual

magnets. The Douglas Hospital Research Centre will be purchasing such a scanner over the next 8 months.

General procedure

Six-month home interview: First visit (90 minutes)

Mother

1. Questionnaires (Time required for completion is approximately 90 minutes)

1.1 Stress:

1.1.1. Perceived Stress Scale. Maternal stress measures are assessed at 6 and 12 months postpartum. Perceived stress is assessed using the short form of the Perceived Stress Scale (4 items) (Cohen et al. 1983). The short form has an internal consistency of .72 (coefficient alpha) and two month test-retest reliability of .55.

1.1.2. The Parental Stress Scale, (Berry and Jones, 1995) is an 18-item scale, which has good internal reliability (alpha = .83) and good 6-week test-retest stability (.81). This scale is much shorter than the Parenting Stress Index and is especially useful when samples include parents whose child does not have a developmental disability.

1.1.4 Chronic stressors are assessed via measures of money problems, food security, housing problems, work stress, negative interactions with others and conjugal violence. The money problem questions were drawn from the Daily Hassles Scale (Kanner et al., 1981). Each woman is asked if, since the beginning of their pregnancy, they have lacked money to: (1) pay for housing, (2) pay for electricity, hot water or heating, (3) buy food, (4) buy prescription medications, (5) buy or pay for anything else that she or her family needs.

1.1.5. Work stress is assessed with a 13-item abbreviated version (Fenster et al., 1995) of the Karasek Job Content Questionnaire (Karasek et al., 1986). This measure includes four items on job demands and five items on job control as well as four items on social support at work.

1.1.6. The negative interactions measure asks the first name and relationship of each person with whom the woman can expect to have unpleasant disagreements or to be made angry or upset. The woman also indicates the number of times in the past two weeks that she has had a disagreement with each of these people. This is taken from the Arizona Social Support Interview Schedule (ASSIS) (Barrera M., 1981).

1.1.7. The Marital Strain Scale (Pearlin et al., 1978) is used to assess chronic stress with one's romantic partner. The 9 items represent the three items with the highest factor loadings for each of the three factors contributing to the measure of marital strain. In addition, the Abuse Assessment Screen is used to assess conjugal violence. This five-item instrument assesses the frequency, severity, perpetrator, and body sites of injury (McFarlane et al., 1992; Parker et al., 1993).

1.1.8 Lazarus and Folkman's measure of primary appraisals (of challenge, threat, and centrality) is administered (14 items) (Folkman and Lazarus, 1985).

1.1.9 Reactive responding. This is a 9 items scale that we obtained from [name] based on her work with the MacArthur Network on socioeconomic status and health. The idea is that those who have experienced chronic stress develop a hypervigilant response style to ambiguous environmental stimuli.

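### The 2004 IUGR and control groups are given as single gram bands but described by weight for gestational age; if the gram bands govern, the contrast partly mixes growth restriction with shorter term gestation

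*Combined protocol and SAP*

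**What the plan says.** Combined protocol and SAP, III. Methods, Participants:

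- The only numerical entry limits are in grams: "IUGR, n= 120; 2200-2750 g at birth" for cases and "controls, n= 120; 3000-3500 g at birth" for controls. Neither band carries a gestational week.
- The groups are said to rest on a Canadian reference for birth weight by gestational age, which, the text says, "indicates that the birth weight of 2,750 g represents the 10th percentile, with a weight of 3750 g at the 70th percentile". No week is given for either percentile, and 3750 g is not a limit of either group.
- Gestation enters once, as a restriction: "All babies in this study will be born at > 37 weeks gestation to avoid the complication of prematurity and growth restriction".
- The labels are by weight for age. The recruitment ratio is "two infants of normal birth weight for each infant that is small for gestational age", and the recruitment paragraph says "Two, normal weight for age babies born on the same or closest day to the IUGR baby will be used as controls".
- The parent study measures "predictors of gestational length, which is the outcome measure in this project", so gestational length is already recorded.

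Section IV tests the hypotheses by regression, ANOVA and interaction tests, followed by multilevel and structural equation models. It lists no covariates, so a gestational-age term is neither specified nor excluded.

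The later 72-month Protocol defines prenatal adversity as birth weight corrected for gestational age (Background and rationale). It groups children by percentile for gestational age, 0-20, 21-40 and 41-70% (Analyses, Hypothesis 1), and says these groupings have already been used for tests of attention and impulse control.

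**The concern.** A gram band and a percentile for gestational age are different rules, and they disagree whenever birth weight rises with week. Under a fixed upper limit of 2,750 g, an early-term baby of ordinary size for its week can enter as a case. A later-term baby that is small for its week but heavier than 2,750 g cannot. Controls are chosen by birth date, which does not balance gestation.

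The central hypothesis (II. Hypotheses) is that the postnatal environment determines how fetal adversity affects neurodevelopment. If the gram bands define fetal adversity, an IUGR-control contrast on the 6- to 36-month measures, or an IUGR by postnatal-environment interaction, partly compares shorter with longer gestation within term. The 37-week restriction shows that the plan wants gestation kept apart from growth restriction. It narrows the spread of gestation but does not remove it.

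**Working it through.** **What can be checked from the documents.** The expected case count reproduces: 126 x 0.70 = 88.2, matching "we will obtain a sample of 88 IUGR children and their mothers". The percentile statement cannot be reproduced, because the reference tables are not in the documents. A normal curve through both stated percentiles has SD = (3750 - 2750)/(0.524 + 1.282) = 554 g and mean = 2750 + 1.282 x 554 = 3460 g. On that curve 2200 g is the 1.1th percentile, so the case band holds 10.0 - 1.1 = 8.9% of births. A 10th-percentile rule with the same floor would also hold about 8.9%. The 9% IUGR prevalence quoted for recruitment therefore does not show which rule was meant.

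**Illustration of size.** The documents give neither the weekly weight gain nor the spread of births over weeks, so both are assumed.

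- Assumed week shares p_w for weeks 37-41: 7/18/29/32/14% (mean week 39.28).
- Assumed gain g: 0, 50, 100 or 200 g per week.
- Week mean: mu_w = m + g x (w - 39.28), with a common SD s.
- m and s solve sum p_w Phi((2750 - mu_w)/s) = 0.10 and sum p_w Phi((3750 - mu_w)/s) = 0.70. This gives m of about 3460 g and s = 554/551/542/504 g for the four gains.

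Example at 100 g per week:

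- Week 37 mean = 3460 - 228 = 3232 g, so 2,750 g is at Phi(-482/542), the 18.7th percentile.
- Week 41 mean = 3460 + 172 = 3632 g, so 2,750 g is at Phi(-882/542), the 5.2th percentile.
- Over the five weeks, 2,750 g falls at the 18.7/14.2/10.4/7.5/5.2th percentile.
- Share of the case band not below its own week's 10th percentile: f = sum p_w max(0, F_w(2750) - 0.10)/0.0885 = (0.07 x 0.087 + 0.18 x 0.042 + 0.29 x 0.004)/0.0885 = 0.0148/0.0885, about 17%.

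All four gains:

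| Assumed gain, g/week | 0 | 50 | 100 | 200 |
|---|---|---|---|---|
| Case band not below own week's 10th percentile | 0% | 8% | 17% | 34% |
| The same, of 88 expected cases | 0 | 7 | 15 | 30 |
| Small babies (2,200 g or more) missed above 2,750 g | 0% | 8% | 17% | 34% |
| Weeks 37-38, cases | 25% | 31% | 38% | 53% |
| Weeks 37-38, controls | 25% | 26% | 27% | 28% |
| Gestation gap, controls minus cases (weeks) | 0 | 0.15 | 0.31 | 0.65 |
| Dilution, outcome linear in own-week z-score | 0% | 1% | 3% | 12% |
| Dilution, effect only below own 10th percentile | 0% | 8% | 17% | 36% |

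The missed row takes as its base small babies of 2,200 g or more, since the floor is deliberate. It equals the first row because both rules admit about 8.9% of births.

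Linear dilution is 1 - (mean z gap under gram bands)/(mean z gap under percentile groups with the 2,200 g floor). At 100 g it is 1 - 1.261/1.297 = 3%. At 200 g it is 1 - 1.162/1.318 = 12%. Threshold dilution is f plus the share of controls below their own week's 10th percentile. That control share is at most 2% in this fit.

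**Sensitivity.**

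- Three other assumed week distributions (4/12/26/36/22, 12/24/31/24/9 and 20% each), at 50/100/200 g: f is 8-11/17-22/35-44%, and the gap is 0.14-0.23, 0.30-0.46 and about 0.6-0.9 week. With equal shares at 200 g, the share of controls below their own 10th percentile rises to about 5%.
- Week 38 onward only, at 0/50/100/200 g: f is 0/8/15/30% and the gap is 0/0.11/0.22/0.43 week.

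Confounding from the gap itself would equal the gap times the outcome change per week of gestation, which the documents do not give.

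**The case against.** The case for leaving this alone has real force. The gram bands are the only numerical rule, so the weight-for-age wording may be loose description. Section IV names no IUGR-control contrast, and its one power calculation relates two continuous variables, maternal sensitivity and cortisol response, so it is untouched. No covariate of any kind is listed, so the missing gestational-age term is part of a general brevity. The investigators later adopted percentile groupings and say they had already used them for attention and impulse-control tests. With about 600 children enrolled by then, rewriting entry criteria would change little. The Protocol's background also describes risk as rising progressively as birth weight falls, which favours the mild linear dilution over the threshold figures. Finally, maternal adversity may act partly through shorter gestation, so whether to adjust for gestation depends on the effect intended.

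Most of this limits the size and reach of the point; it does not remove it. If the gram bands governed, the labels are inaccurate and the mixing follows whenever weight rises with week. The two-group design implies some group comparison, and the later Protocol does not amend how the 2004 groups enter the 6- to 36-month analyses.

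A reader might infer that about a third of the cases were not growth restricted, or that the 2004 results are biased to that degree. The documents do not support this. The one-third figure needs an assumed 200 g per week, and it counts babies just above a 10th-percentile line as wholly misclassified. Nor do the documents show that the gram bands were in fact applied against the weight-for-age labels.

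**Conclusion.** The point holds in conditional form. The 2004 text gives two rules for the same groups and does not say which decides. If it is the gram bands, and if birth weight rises with week within term, IUGR status carries some gestational age with it, and neither the matching nor section IV corrects for that. The direction follows from those two conditions alone. The size rests on assumed weekly gain and week shares: from zero to a gestation gap of about 0.65 week in the main illustration, with dilution of 0 to 12% under a graded outcome and more only under a sharp threshold.

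The 72-month analysis is unaffected, as is any earlier analysis that already used the percentile groupings. It would also go too far to say that the plan rules out adjustment for gestation; it is silent. Priority is minor to moderate.

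**What to change.** 1. Reconcile the two descriptions in III. Methods, Participants. State whether grams or percentile for gestational age defined the groups, what the percentile limits are, and whether week 37 counts.
2. In every analysis of the 2004 cohort that uses IUGR status or birth weight as the prenatal exposure, classify by gestational-age-specific percentile or z-score from the reference already cited, as the 72-month Protocol does. State any cut-off used, because the 0-20/21-40/41-70% groupings do not include a 10th-percentile cut.
3. If the gram-band groups are kept for any comparison, adjust that comparison for gestational age.
4. Report as a limitation that reclassifying enrolled children cannot recover small babies who were never enrolled because they weighed more than 2,750 g.

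The cost is a percentile lookup and at most one covariate. Gestational length is the parent study's outcome, so no new data are needed.
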